## 5 Sequence of Planned Analysis

### 5.1 Interim Analysis

AEs and SAEs are being monitored on a regular basis by a Data and Safety Monitoring Committee (DSMC). No interim futility or efficacy analyses are planned.

### 5.2 Final Analyses and Reporting

All final planned analyses identified in the research plan and in this SAP will be performed only after the last patient has completed assessments scheduled for the length of the study period and the database has been cleaned and locked. Any post-hoc exploratory analyses performed to provide support for planned analyses but not identified in this SAP will be documented and clearly identified as unplanned analysis in the manuscript.

## 6 Statistical Methods

### 6.1 Analysis Populations

- Intent-To-Treat [ITT] population: All randomized participants.
- Per-Protocol (PP) population: Excluding babies not following the protocol.
- Subset Populations: Hypoxic-Ischemic Encephalopathy (HIE); Cooled/not cooled

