It should be remembered that this was the response rate to LEV used as a *second* line agent in subjects refractory to PB as a first line agent. As such this response rate of 42% seen in the higher dose cohort compares favorably with efficacy data for phenytoin and Phenobarbital when used as second line agents. Painter et al. found that of 4 of 17 (24%) neonates with seizures refractory to Phenobarbital responded to the phenytoin as the next AED, and 5 of 16 (31%) neonates with seizures refractory to phenytoin responded to Phenobarbital as the next AED ⁶³.

Two recent publications document retrospectively the response of neonatal seizures to IV LEV. Abend et al. reported that 23 neonates treated with LEV at a low mean initial dosage of 16 mg/kg had a >50% seizure reduction in 35% of infants with seizure termination in 7 of 23 (30%) ⁶⁸. No respiratory or cardiovascular effects were detected. Khan et al. reported that 22 neonates received an LEV load of 10-50 mg/kg and 22 (86%) achieved immediate seizure cessation at 1 hour. No serious side effects were evident; one infant became irritable on treatment responding to 50mg of pyridoxine ⁶⁹.

8. RESEARCH DESIGN AND METHODS: (guideline length is 3-6 pages)

Study Design Summary:

[figure not shown]
This study will be a phase II preliminary efficacy, dose escalation and safety study. The study design will be a randomized blinded controlled treatment study. Infants recognized as having neonatal seizures or as being at risk of developing seizures will be recruited and started on continuous video EEG monitoring. The EEG data will then be reviewed continuously for electrographic seizures by study investigators, along with remote continuous EEG monitoring by Corticare technicians. A novel seizure detection algorithm operating in near-real time will be compared to the real-time continuous EEG reading.

Once eligibility and consent are confirmed, patients will be randomly assigned to the LEV or control treatment group in a 60:40 allocation ratio, stratified by site.

Blinding will be maintained by appropriate dilution of LEV and Phenobarbital such that the same volume (ml/kg) loads are given to both treatment groups.

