Subjects randomised to receive LEV will, at the onset of electrographically confirmed seizure activity, receive an intravenous loading dose of LEV of 40mg/kg given over 15 minutes. If electrographic seizures are confirmed to persist or recur more than 15 minutes after the first infusion is complete, a further 20mg/kg load of LEV will be administered IV over 15 minutes. Maintenance LEV at 10 mg/kg/dose will be given IV q8 hours and continued for at least 5 days. If seizures persist or recur more than 15 minutes after the second LEV infusion is complete, a PB loading dose of 20 mg/kg will be administered IV over 15 minutes. If seizures persist or recur more than 15 minutes after the first loading dose of PB is complete, a second 20mg/kg load will be administered IV over 15 minutes. This will result in PB being started within 1 hour of the onset of seizures if and when loading with LEV is ineffective. Patients given any PB loading doses will be started on maintenance PB with 1.5 mg/kg/dose given IV q8 hours and continued at least until the end of the study

Figure 2 details the study flow.

Subjects randomized to the control group will, at the onset of electrographically confirmed seizure activity, receive an intravenous loading dose of PB of 20 mg/kg given over 15 minutes. If electrographic seizures are confirmed to persist or recur more than 15 minutes after the first infusion is complete, a further 20mg/kg load of PB will be administered IV over 15 minutes. Maintenance PB at 1.5 mg/kg/dose will be given IV q8 hours and continued for at least 5 days. If seizures persist or recur more than 15 minutes following the second PB infusion, a 40 mg/kg load of LEV will be administered IV over 15 minutes. If seizures persist or recur more than 15 minutes after the first loading dose of LEV is complete, a second 20mg/kg load of LEV will be administered IV over 15 minutes. Patients given an LEV loading doses will be started on maintenance LEV with 10 mg/kg/dose given IV q8 hours and continued at least until the end of the study.

If electrographic seizures are still apparent following treatment with both LEV and PB, or if they recur during the 5 days during which the study protocol is active, the patient will be considered to have failed the experimental treatment regime and institutional specific standard seizure management will dictate the ongoing

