Expected enrollment: We plan to treat 100 subjects over 4 years and based on our prior PK study experience we anticipate needing to recruit, consent and monitor 300 subjects to yield this number, (a conservative estimate). Randomization will be carried out with a six to four ratio so that 60 subjects will receive treatment with LEV and 40 will receive standard treatment with Phenobarbital treatment. Each site will treat 4 to 6 subjects with seizures each year, recruiting and monitoring up to 13 infants per year in order to yield these numbers. Historical data from the past 3 years in each of four neonatal intensive care units indicate that we will be able to recruit these numbers of patients easily: Rady Children's Hospital have treated on average 39 term infants with seizures per year over the past 3 years, Auckland Hospital NICU have treated on average 12 per year, Oakland Children's Hospital have treated 6-10 per year. In our prior PK study we recruited 36 subjects with neonatal seizures in 18 months, (18 of whom were refractory to PB and therefore received study drug).

Data to be collected:

Clinical Data: Demographic and clinical data will be collected, including birth weight, gestational age at birth, postnatal age, gender, pregnancy history, family medical history, mode of delivery, Apgar scores, and cord blood gas if available. Etiology of seizures will be recorded. Where etiology is unknown, results of neuroimaging, blood, urine metabolic and CSF studies will be reviewed. A record of all medications received by the infant will be kept. Case report forms will be developed to facilitate data entry from all sites into the REDcap data management system available to us through the UCSD Clinical and Translational Institute (CTRI).

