There is sufficient evidence of efficacy and safety to justify study of LEV as a first line agent. LEV has good efficacy in other populations, including in populations experiencing refractory status epilepticus. In neonates there are accumulating reports of its efficacy in cases where seizures are refractory to multiple other agents. Our preliminary analysis of efficacy when LEV is used as a second line agent suggests efficacy similar to that of Phenobarbital and phenytoin when used as second line agents (as described above).

Our study design ensures rapid escalation to treatment with Phenobarbital in subjects who do not respond to LEV. Additionally, because our study will utilize real time monitoring of continuous EEG recordings leading to more rapid detection and treatment of electrographic seizures than is normally standard of care, our study subjects will receive AED treatment in a shorter time frame than is usual.

Plan for Statistical Analysis

General considerations: The general objectives of this study are to gain preliminary evidence of efficacy of LEV in neonates, to determine if a phase III trial is warranted, and if so, and to obtain to obtain sample size estimates for that study. In addition further safety data in this population is required. This study will allow the LEV and PB groups to be compared with respect to (a) preliminary evidence of efficacy, and (b) safety. All analyses will incorporate the intention-to-treat principle; all randomized participants will be included in the analysis. Analyses for all efficacy outcomes will be guided by descriptive and exploratory analyses. All results will be reported as point estimates (proportions or mean differences across groups, as appropriate) and interval estimates (95% confidence intervals) with two-sided p-values denoting statistical significance. Since this is a phase II preliminary efficacy and safety study, no adjustments for multiple comparisons will be made and a p-value of 0.05 will be considered statistically significant.

Analysis Plan for Aim 1: Evaluating efficacy in seizure cessation

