300 subjects will be recruited in total from the 5 NICU's over 4 years. A higher than anticipated screening to treatment ratio of approximately 3:1 monitored to treated neonates has occurred in the initial 85 neonates recruited to this study. The originally anticipated 2:1 EEG monitoring: treatment ratio is likely lower due to the beneficial effects of hypothermia treatment many neonates receive as a usual standard of care. Hypothermia treatment may be reducing the incidence of seizures in this population. This change in ratio may also be a reflection of a benefit of this study in that behavior in a few neonates which may have previously been clinically judged to reflect seizure activity, because of continuous EEG monitoring viewed by EEG technicians in this study also reviewed by a neurologist, have been correctly diagnosed as myoclonic jerks rather than seizures. This has thereby prevented some neonates from receiving medication for seizure treatment because their behavior is not confirmed by their EEG as seizure activity. For these reasons an increased number of total subjects will be needed in this study in order for 100 subjects to be treated.

Inclusion Criteria:

Term newborns admitted to the UCSD, Children's Hospital and Research Center Oakland, Auckland Hospital, Rady Children's Hospital or Sharp Mary Birch NICUs with seizures or at risk for seizures:

- Term infants (gestational age greater than or equal to 36 weeks)
- Postnatal age < 14 days.
- Serum creatinine equal to or less than 1.6 mg/dL at time of enrollment
- Are still experiencing either clinical or electroencephalographic seizures or are at risk for neonatal seizures.
- For whom parental consent to participate in the study is obtained.

Exclusion criteria:

- Biochemical abnormality – hypoglycemia, hypocalcemia- that when treated result in seizure cessation.
- Severe hypoxic ischemic injury likely to result in imminent death
- Infants with a birth weight less than 2200 g would be excluded the study. This is the new recommended 10th percentile for 36 weeks gestation. The blood drawn at any one time will be <3 mls/kg which remains within the NIH guidelines for pediatric blood draws.

Patients of all ethnic groups will be included in the study. Based on the patient population our group treats, most patients will be European or Hispanic. Both male and female infants will be recruited to the study.

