### 6.2 Multiple Comparisons and Multiplicity

Tests of group differences (active LEV compared to the control PB group) for the primary outcome will be conducted at a two-sided alpha level of 0.05. Similarly, other secondary outcomes will also be conducted using a two-sided alpha level of 0.05. No adjustment for multiple comparisons will be used in this study; however, all results will be reported using point estimates with the corresponding 95% confidence intervals.

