## 7.5 Analysis of Safety Outcomes

Adverse Event and Serious Adverse Events will be tabulated by randomization group and by drugs received, respectively. Details including seriousness, intensity, causality, withdrawal due to event and outcome will be summarized by frequencies and percentages by randomization group and by drugs received. Fisher's exact tests will be used to compare rates of adverse events, serious adverse events, study discontinuation and deaths between randomization group and by drugs received, respectively.

Findings will be tabulated by randomization group overall and for findings marked as AE and SAE, respectively.

Safety Labs (using DAIDS guidelines) will be presented with shift tables (hour 48 vs baseline) by randomization group and by drugs received, respectively.

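### The SAP names no safety population of dosed infants, so the between-arm safety tests can include infants who were randomised but never given study drug (minor)

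*SAP*

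**What the plan says.** SAP 6.1 lists three kinds of population: "Intent-To-Treat [ITT] population: All randomized participants", a per-protocol set, and subsets by hypoxic-ischemic encephalopathy and cooling. The per-protocol set does not isolate dosed infants, because an infant who never seizes and is never dosed has still followed the protocol. The protocol's Plan for Statistical Analysis (section 8) is equally broad: "All analyses will incorporate the intention-to-treat principle; all randomized participants will be included in the analysis".

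For safety, SAP 7.5 states that "Fisher's exact tests will be used to compare rates of adverse events, serious adverse events, study discontinuation and deaths between randomization group", and repeats the comparison by drugs received. No denominator is given. SAP 6.2 adds that "all results will be reported using point estimates with the corresponding 95% confidence intervals".

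On timing, the Study Design Summary in protocol section 8, which SAP 3.1 repeats, says: "Once eligibility and consent are confirmed, patients will be randomly assigned to the LEV or control treatment group". Being at risk is enough to be eligible; the inclusion list in protocol section 10 admits infants who "Are still experiencing either clinical or electroencephalographic seizures or are at risk for neonatal seizures". For infants whose first sign of illness is a seizure (Group C), protocol section 10 places randomisation during EEG set-up. Dosing comes later: LEV infants "at the onset of electrographically confirmed seizure activity, receive an intravenous loading dose of LEV of 40mg/kg", and PB infants start their first load at the same trigger. On numbers, protocol section 8 plans 100 treated infants and says "we anticipate needing to recruit, consent and monitor 300 subjects to yield this number".

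**The concern.** In many trials nearly every randomised patient is dosed, and the lack of a separate safety set does little harm. Here the two sets can differ, because the event that triggers dosing comes after randomisation and many monitored infants never have it. If never-dosed infants enter both arms of a safety test, they cannot show any effect of either drug. They add denominators, and possibly background events, to both sides.

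Safety is Aim 4, and the trial is meant to inform a decision on a phase III study. A LEV-PB difference in treated infants could be reported as smaller than it is, with a narrower interval because the sample is larger. The tests by drugs received are not diluted in this way. They cannot take the place of the randomised comparison, however, because an infant receives both drugs only if the first-line drug failed, so those groups are defined by response.

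**Working it through.** **Inputs from the documents**
- 100 treated, split 60 LEV and 40 PB, and 300 recruited (protocol section 8, Expected enrollment).
- About 3:1 monitored to treated in the first 85 infants (protocol section 10). Protocol section 4 still implies 2:1, with 50 recruited and 25 treated per year.
- Two-sided 0.05 and Fisher's exact test (SAP 6.2 and 7.5).

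**Inputs assumed.** The documents give no adverse-event rates by arm. Two illustrations are used for dosed infants: 25% LEV against 50% PB, and 10% LEV against 30% PB. The event rate q in never-dosed infants is taken as equal in both arms.

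**The plan's own figures.** Recruitment: 100 × 3 = 300, as stated. Power for 60 and 40 infants at 22% against 50%: 83.1% by the uncorrected chi-square test and 79.6% by exact Fisher enumeration. The stated 80% is therefore consistent with the planned test at 60 and 40.

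**Dilution.** Let f be the dosed share of those randomised, equal in both arms, and let pL and pP be the event rates in dosed infants. Then

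RD(all randomised) = [f·pP + (1 − f)·q] − [f·pL + (1 − f)·q] = f·(pP − pL).

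The rate q cancels, so the factor on the risk difference is f whatever the background rate:
- only treated infants count as randomised: f = 100/100 = 1, no loss;
- 2:1: f = 100/200 = 0.50;
- all 300 randomised: f = 100/300 = 0.33.

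**Example, 25% against 50%, no events in never-dosed infants**

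| Infants analysed | LEV rate | PB rate | Difference (points) | Fisher power |
|---|---|---|---|---|
| Dosed only, 60 and 40 | 25% | 50% | 25 | 68% |
| 2:1, 120 and 80 | 12.5% | 25% | 12.5 | 60% |
| 3:1, 180 and 120 | 8.3% | 16.7% | 8.3 | 57% |

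The expected event counts are the same in every row: 60 × 0.25 = 15 on LEV and 40 × 0.50 = 20 on PB. Only the denominators grow, so the risk ratio stays at 0.5.

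Expected Wald intervals:
- dosed only: standard error √(0.25·0.75/60 + 0.50·0.50/40) = 0.0968, interval 25 ± 19, or 6 to 44 points;
- 3:1: standard error √(0.0833·0.9167/180 + 0.1667·0.8333/120) = 0.0398, interval 8.3 ± 7.8, or 0.5 to 16 points.

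**Second example, 10% against 30%, no events in never-dosed infants.** Power is 67% in dosed infants and 62% at 3:1.

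**If never-dosed infants do have recorded events.** With q from 10% to 30% at 3:1, power is 41% to 30% in the first example and 36% to 23% in the second. These values of q are assumptions with no support in the documents.

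**The case against.** The strongest reply is that the trial may never have meant to count undosed infants as randomised, and much of the text fits that reading:
- Protocol section 8 links the six-to-four allocation directly to 60 and 40 treated infants, and the power statement uses those numbers.
- Protocol section 10 presents 3:1 as a ratio of screening to treatment.
- The Add on Study paragraph in protocol section 8 treats at-risk infants without seizures as a parallel group beside the treated ones.
- SAP 7.1 counts enrolled and randomised infants separately.
- The primary outcome in SAP 4.1 is timed from treatment and has no clear meaning in an infant with no seizure and no drug.

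This stands as far as size is concerned. A reader might infer that the safety difference will be cut to one third, but no section says that all 300 are randomised. It does not close the gap, because no section makes randomisation wait for a seizure, and the passages on timing say otherwise.

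A second reply concerns background events. Protocol section 8 (Safety data) ties vital signs to infusions and adverse-event documentation to treatment phases. The daily examinations in protocol section 14 appear under monitoring for drug reactions during treatment. Safety capture is thus largely linked to dosing, which makes the larger power losses speculative. This also stands.

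A third reply concerns coverage. In the first example, an all-randomised interval at 3:1 contains the dosed-infant difference of 25 points in only 0.4% to 14% of trials, and a reader might call the interval invalid. That compares it with a different estimand. In the same scenarios it covers its own target in 95% to 98% of trials. The low figures restate the assumed dilution and are not a further harm.

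Finally, the drugs-received tables in SAP 7.5 would make undosed infants visible, which softens the consequence. They do not supply an undiluted comparison by randomised arm.

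**Conclusion.** The omission is real: no safety population is defined, and as written the between-arm safety tests can take in infants who never received study drug. Its size depends on a number that the documents do not give. The risk difference is multiplied by the dosed share of those randomised: 1 if only treated infants count, about one half at 2:1, and about one third only if all 300 are randomised. This assumes equal dosed shares and equal background rates across arms, which is reasonable in expectation because the dosing trigger precedes any study drug.

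With no events in never-dosed infants, the power loss at 3:1 is modest (68% to 57%, or 67% to 62%, at the assumed rates) and the risk ratio does not change. The documents do not support a firm claim that a safety signal would be hidden. This is a minor point about an unstated denominator that is easily settled.

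**What to change.** In SAP 6.1, add a safety population: infants who started a first study-drug infusion, grouped by randomised arm. Because dosing is triggered by an EEG-confirmed seizure under blinding and before any study drug, this restriction keeps the arms comparable.

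In SAP 7.5, run the between-arm tests of adverse events, serious adverse events and deaths in that population, counting events from the first infusion. Tabulate any never-dosed randomised infants separately, and keep the drugs-received tables as descriptive.

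The cost is a few lines of SAP text and a filter on first infusion, with no new data. The downside is that events in never-dosed infants move from the test to a table. If only treated infants were ever counted as randomised, the change alters no result.

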### 6.2 Multiple Comparisons and Multiplicity

Tests of group differences (active LEV compared to the control PB group) for the primary outcome will be conducted at a two-sided alpha level of 0.05. Similarly, other secondary outcomes will also be conducted using a two-sided alpha level of 0.05. No adjustment for multiple comparisons will be used in this study; however, all results will be reported using point estimates with the corresponding 95% confidence intervals.

### 6.3 Covariates

Covariate adjustment will be specified for each analysis in their respective sections in this SAP, as applicable.

CONFIDENTIALITY STATEMENT: This report from the USC Alzheimer's Therapeutic Research Institute (ATRI) is for the sole use of the intended recipient(s) and contains confidential and privileged information. Any unauthorized review, use, disclosure, copying or distribution is strictly prohibited.

## 6.4 Data Management and Analysis Software

All analyses will be performed using R statistical software (<http://www.r-project.org>). The R version used will be specified in the analysis reports and will be reported in all manuscripts.

# 7 Statistical Analysis

## 7.1 Study Flow

A CONSORT style flow diagram will illustrate patient progression through the trial from enrollment to completion of the final primary outcome assessment. Number (percentage) will be included for neonates enrolled, randomized, study discontinued (with reasons), analyzed, excluded from analysis (with reasons). The diagram will be separated by treatment groups starting from randomization.

## 7.2 Patient characteristics and baseline variables

Baseline demographics and clinical characteristics will be summarized by frequencies and percentages for categorical variables, continuous variables will be summarized by mean and standard deviation as well as quartiles. Group comparisons will be performed using Wilcoxon-rank sum test for continuous variables. Fisher's Exact test will be used for categorical data. The following baseline demographic and clinical characteristics will be presented:

- Demographics
  - Gender
  - Race
  - Ethnicity
  - Family Medical History of Seizures or Neurological Abnormality
  - Pregnancy (Normal/Abnormal)
  - Delivery Situation
  - Mode of Delivery
  - Did Mother Have Anesthesia?
  - Delivery Presentation
  - Birth Weight
  - Head Circumference at Birth
  - Gestational Age at Birth
- Clinical
  - Cord PH
  - APGAR Scores at 1, 5 and 10 min
  - Seizures etiology

